9. STUDY ENDPOINTS

9.1. The primary outcomes:

- **Efficacy endpoint**

- 1- Change in WHO Ordinal Scale for clinical improvement (baseline to end of study will be measured on days 1,7,14 and 28).

The World Health Organization (WHO-WHO) has proposed the “Ordinal Scale of Clinical Evaluation of the World Health Organization” presented below as a means of generating a numerical value to assess the health status of the participant to allow comparisons to be made in clinical studies. The scale is shown in the table below and will be used to assess a secondary effectiveness target in this study.

Patient State	Descriptor	Score
Uninfected	Uninfected; no clinical evidence and viral RNA detected	0
Ambulatory	Symptomatic; independent	1
	Symptomatic; assistance needed	2
Hospitalized: Moderate diseases	Hospitalized, no oxygen therapy	3
	Hospitalized; oxygen by mask or nasal prongs	4

	MGC Pharma Clinical Study Protocol	Protocol No.: MGC-009
		Version 02, 05 Sep 2021
		Page 34 of 76
A Phase IIb, double blind, placebo-controlled clinical study designed to evaluate the effect of CimetrA in patients diagnosed with COVID-19		CONFIDENTIAL

Hospitalized: Severe diseases	Hospitalized; oxygen by NIV or high flow	5
	Hospitalized; mechanical ventilation	6
	Mechanical ventilation and vasopressors, dialysis or ECMO	7
Dead	Dead	8

2- Change in COVID-19-Related Symptoms score (measured on days 1,7, 14, 28)

• **Safety Endpoints**

Safety will be assessed through collection and analysis of adverse events, blood and urine laboratory assessments and vital signs.

9.2. **The secondary outcomes:**

- Number of participants with depending on oxygen supplementation through day 28 since onset of symptoms
- Change in inflammatory marker levels - IL-6, IL-1 β , IL-12, TNF α , IFN- γ , CRP, NLR (Neutrophil / Lymphocyte ratio) (days 1, 2, 4, 7) compared to baseline
- Pharmacokinetic profile of the study drug on day 1 through 24 Hrs.
- Incidence and duration of mechanical ventilation
- Incidence of Intensive Care Unit (ICU) stay during COVID-19 complication
- Percentage of participants with definite or probable drug related adverse events
- Long term adverse events of COVID-19 on Day 28
- The Impact covid_19 on quality of life of patients on Days 1, 14 and 28

9.3. **The exploratory outcomes:**

- Course of change in D Dimer levels compared to baseline

	MGC Pharma Clinical Study Protocol	Protocol No.: MGC-009
		Version 02, 05 Sep 2021
		Page 35 of 76

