It is important to say that both active ingredients of the study drug is defined as GRAS and found to be safe with no adverse events in clinical studies. Based on the literature, the following data regarding the potential risks of the Curcumin and Boswellia is available –

1. Madhu K at al., Rahmani et al. and Selvi et al. reported gastrointestinal adverse events related to diarrhea, nausea and abdominal pain
2. Chuengsamarn et al. reported hot flashes and constipation that were observed in the clinical trial in type 2 diabetes patients .

14. **ADVERSE EVENT**

14.1. **Definition of adverse event**

Adverse event means any untoward medical occurrence associated with the use of a drug in

	MGC Pharma Clinical Study Protocol	Protocol No.: MGC-009
		Version 02, 05 Sep 2021
		Page 55 of 76
A Phase IIb, double blind, placebo-controlled clinical study designed to evaluate the effect of Cimetra in patients diagnosed with COVID-19		CONFIDENTIAL

humans, whether or not considered drug related.

An Adverse Event (AE) is any untoward medical occurrence in a subject administered a pharmaceutical product, whether it is related to the pharmaceutical product in question or not. This includes a change in a subject's condition or laboratory results, which has or could have a deleterious effect on the subject's health or well-being.'

In this study, local reactions due to study treatment will be captured in the diary, and this information will not be duplicated in the CRFs.

AEs to be recorded in the CRFs are systemic reactions that also are captured in the diary and other AEs occurring that are not due to study treatment.

14.2. **Methods for eliciting AEs**

All subjects should be carefully monitored for occurrence of AEs during the study and for a reasonable time period thereafter. No distinction should be made between the investigational treatment and the placebo treatment for the purpose of AE reporting.

All directly observed and spontaneously reported AEs should be recorded in the CRF. If no AE has occurred during the study period, this should also be recorded in the CRF. In addition, each study subject will be asked an open question about possible AEs at each clinic visit following initiation of treatment.

The following evaluations are to be done by the Investigator in connection with the AE:

- type of event
- seriousness
- degree of severity
- duration (start - end)
- action taken

	MGC Pharma Clinical Study Protocol	Protocol No.: MGC-009

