The completed CRFs should be made available for checking of accuracy by the Clinical Monitor as agreed in advance. The original CRFs are the sole property of the MGC-Pharma and should not be copied or made available in any form to a third party, with the exception of authorized representatives of local Regulatory Authorities, without written permission from MGC-Pharma.

15.2. **Source Data**

The printouts from the laboratory analysis will be considered as source and must be labeled with the subject number and measurement period. The printouts must be dated and signed by the Investigator. Results from the blood pressure, heart rate, weight and height measurements are to be recorded directly into the CRF. The subject diary is part of the CRF. Copies of the clinical laboratory and hematology data will be stored in the subject records.

	MGC Pharma Clinical Study Protocol	Protocol No.: MGC-009
		Version 02, 05 Sep 2021
		Page 59 of 76
A Phase IIb, double blind, placebo-controlled clinical study designed to evaluate the effect of CimetrA in patients diagnosed with COVID-19		CONFIDENTIAL

Signed Informed Consent Forms, the existence of medical notes, inclusion/exclusion criteria and AE/SAE will be checked in 100% of the CRFs.

Source data verification

On site subject charts, outside laboratory reports and outside notes, including MD notes, letters and follow-up to subjects/families, are used to verify CRF data. At least 30% of source documents will be verified during the study as follows:

- ☐ 100% of the source documents for the first two visits of the first eight study subjects.
- ☐ 30% source verification for all visits of all subjects.
- ☐ 100% source verification for inclusion/exclusion criteria for all subjects.
- ☐ 100% source verification for adverse event assessment for all subjects.
- ☐ 100% source verification for medication history.

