A Phase IIb, double blind, placebo-controlled clinical study designed to evaluate the effect of CimetrA in patients diagnosed with COVID-19		CONFIDENTIAL

The 3 groups will be compared with the ANOVA test or Kruskal Wallis non-parametric test, following by post-hoc analysis for pairs differences.

Additional Efficacy Parameters of Interest

A count and percentage of participants responding to each of the exploratory efficacy endpoints will be presented. The groups will be compared with a chi-squared test or a Fisher’s exact test.

Safety Analysis

The primary safety variable, the cumulative incidence (and 95% CI) of device related adverse events (AEs) throughout the study, will be presented in tabular format and will include incidence tables by severity.

Serious adverse events, device-related SAEs, adverse events (by type and overall), device-related AE, adverse device reactions and device malfunction rates will be compared between the study arms with a Fisher’s exact test.

Serious adverse events will be listed and discussed individually.

PK test

Actual times of dosing and blood collection at various time points will be recorded in source documents as well as CRF’s. Objectives of PK sampling are to measure values of CimetrA active ingredients in plasma at different time point after first administration of study medications and at different time point after multiple administrations during steady state.

PK samples will be processed and frozen on site. Labels have been prepared for the site again containing patient No., visit No., type of test (PK) and time point. Upon completion of the study, samples will be sent to selected analytical laboratory with dedicated courier service. The PK parameters will be obtained from plasma concentration data for curcumin and boswellia.

	MGC Pharma Clinical Study Protocol	Protocol No.: MGC-009
		Version 02, 05 Sep 2021
		Page 65 of 76
A Phase IIb, double blind, placebo-controlled clinical study designed to evaluate the effect of Cimetra in patients diagnosed with COVID-19		CONFIDENTIAL

Analyses of PK data will be based on the PK Set, which will include all subjects who received at least one treatment and for whom concentration data is available.

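### Sections 14.1 and 14.2 give opposite rules on whether local treatment-related reactions enter the CRF, so the primary safety variable of an oral spray may be undercounted

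*Protocol*

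**What the plan says.** Section 14.1 (Definition of adverse event) sets a recording rule in two sentences. The first is that "local reactions due to study treatment will be captured in the diary, and this information will not be duplicated in the CRFs". The second lists what does go in the CRF: "AEs to be recorded in the CRFs are systemic reactions that also are captured in the diary", together with "other AEs occurring that are not due to study treatment". The one class outside both sentences' CRF list is the reaction that is local and due to treatment.

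Section 14.2 (Methods for eliciting AEs) gives a general rule without that exception: "All directly observed and spontaneously reported AEs should be recorded in the CRF". It also makes severity and likelihood of causality evaluations for the investigator. Section 15.2 (Source Data) adds: "The subject diary is part of the CRF". Under section 10.2.1 the subject fills in the diary, for events between visits.

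Three analyses use the resulting data:

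- Section 17, Safety Analysis: "The primary safety variable, the cumulative incidence (and 95% CI) of device related adverse events (AEs) throughout the study", with incidence tables by severity.
- Section 9.2, a secondary outcome: "Percentage of participants with definite or probable drug related adverse events".
- Section 17: Fisher's exact comparisons between arms of adverse events, both by type and overall, and of related events.

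Section 12.2 states that the product is sprayed into the oral cavity.

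**The concern.** For a product sprayed into the mouth, local oral reactions are the related events tied most directly to the route. They are also the one class that 14.1 keeps off the CRF adverse event record. The primary safety variable is an incidence of related events, and it is the only safety quantity given a confidence interval. If part of its numerator is left out by instruction, the report could show a low related-event rate with a narrow interval although local reactions occurred. Sites that follow 14.2 would enter those same events, so the count would depend on which section a site obeyed. The full source verification of adverse event assessment promised in section 15.2 need not reveal this, because the omission would follow the protocol.

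**Working it through.** **Step 1: the recording rules side by side.**

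| Event | 14.1 | 14.2 |
|---|---|---|
| Systemic reaction | CRF and diary | CRF |
| Event not due to treatment | CRF | CRF |
| Local reaction due to treatment | Diary only | CRF, if observed or spontaneously reported |

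The sections agree on the first two rows and conflict on the third.

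**Step 2: does section 15.2 reconcile them?** If the diary is part of the CRF, a local reaction written there is in the CRF in a formal sense. But 14.1 treats diary and CRF as separate places. The subject completes the diary, while severity and causality are the investigator's under 14.2. A bare diary entry therefore lacks the causality grade needed for the definite-or-probable outcome in section 9.2 and the severity grade needed for the tables in section 17.

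**Step 3: size, by illustration.** There is no figure in the plan to reproduce here, since the protocol gives no local reaction rate. The only planning input is 80 patients per arm (section 17), hence 160 on active drug. Assume a systemic related rate s and an independent local related rate l, with every site following 14.1.

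- True related incidence: t = 1 − (1 − s)(1 − l).
- Expected reported incidence: s.

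With s = 3%:

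- l = 2%: t = 1 − 0.97 × 0.98 = 4.9%
- l = 5%: t = 1 − 0.97 × 0.95 = 7.9%
- l = 10%: t = 1 − 0.97 × 0.90 = 12.7%

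In each case about 3% is reported.

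**Step 4: would the confidence interval reveal it?** Let X be binomial (n, s). The table gives the probability that the exact (Clopper-Pearson) 95% upper limit falls below t.

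| s | l | t | n = 80 | n = 160 |
|---|---|---|---|---|
| 3% | 2% | 4.9% | 9% | 14% |
| 3% | 5% | 7.9% | 30% | 65% |
| 3% | 10% | 12.7% | 91% | 99.7% |
| 10% | 2% | 11.8% | 4% | 7% |
| 10% | 5% | 14.5% | 18% | 36% |
| 10% | 10% | 19.0% | 59% | 88% |

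In the limiting case where every related reaction is local, the reported count is zero whatever the true rate. The upper limit is then 1 − 0.025^(1/80) = 4.5% for one dose arm, or 1 − 0.025^(1/160) = 2.3% for both active arms.

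**The case against.** The strongest reply is that 14.1 only avoids duplication. Section 15.2 makes the diary part of the CRF, so a local reaction is recorded once, and nothing in section 17 restricts the safety tables to a particular CRF page. Which source feeds which table could be left to a statistical analysis plan. Dosing is confined to days 1 and 2 in hospitalised patients, with an adverse event assessment and a physical examination on day 2. Staff would probably see or hear of a local reaction, and 14.2 then sends it to the CRF.

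Part of this stands. A reader might infer that local reactions vanish from the trial, and the documents do not support that: the diary still holds them. What does not stand is that this cures the defect. An analysis plan can choose a source, but it cannot supply an investigator grade that was never made. The likelihood that staff notice the reaction is exactly where 14.1 and 14.2 give opposite instructions.

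A reader might also infer that a mouth bleed could never reach the primary safety variable, given permitted anticoagulants and the anti-aggregant activity credited to curcumin in section 4.1. The protocol names no such event. A bleed could be judged systemic and related, which 14.1 does send to the CRF. One blamed on an anticoagulant is correctly outside a related-event count and still enters the CRF.

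The rates are open to challenge too. Section 13.3 reports no drug-related events in the earlier 50-patient trial, which also used a spray. With 2:1 randomisation and about 33 on active drug (an assumption), none would be seen with probability 0.90^33 = 3% at a 10% local rate; the exact upper limit for 0/33 is 10.6%. That counts against the higher scenarios, though the formulation differed and how that trial recorded local events is not shown.

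Finally, the rule is the same in all arms and the placebo uses the same solvent, so this is undercounting and inconsistency between sites. It is not a demonstrated bias in favour of the drug.

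**Conclusion.** The concern holds as a contradiction in the recording rules with a consequence for safety reporting. If sites follow 14.1, local treatment-related reactions have no graded CRF adverse event entry. They can then drop out of the primary safety variable, the drug-related secondary outcome and the Fisher comparisons. If some sites follow 14.2, the count mixes two definitions.

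The size is not known from the documents. The understatement, from a true 7.9% to 12.7% down to about 3%, rests on assumed rates, independence of local and systemic events, and uniform adherence to 14.1. At local rates of 2% or less the interval would lie wholly below the truth with probability of at most 14% in the cases shown. Serious events are reported under 14.5 and discussed individually, so they are not affected.

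Section 17 words the primary safety variable as *device related*. It is read here as related to study treatment because the product is a drug, but the term is itself wrong and needs correcting. The change is worth making before data collection, since it fixes what sites record; it does not call the efficacy design into question.

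**What to change.** In 14.1, replace the two sentences with one rule: every adverse event, local or systemic and related or not, is entered in the CRF with the investigator's assessment of severity and causality, and the diary serves as a source for those entries. This brings 14.1 into line with 14.2 and leaves 15.2 harmless.

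In section 17, replace *device related* with *study-treatment related* throughout the safety analysis, and state that local reactions are included.

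The cost is two sentences in 14.1 and a wording change in section 17, with no added visit or test. The downside is that sites will have to enter and grade more minor local reactions.

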14.3. Follow-up period after an AE

After an occurrence of an AE, the subject has to be followed up until either the AE has ceased or until the subject is under professional medical care and a potential causality between the study drug and the AE has been penetrated. The post-treatment safety observation period will under AE's resolution or stabilization.

14.4. Definition of Serious Adverse Events

A Serious Adverse Event (SAE) is defined as any untoward medical occurrence that at any dose fulfills at least one of the following criteria:

- is life-threatening
- results in death
- requires hospitalization, initial or prolonged
- results in persistent or significant disability/incapacity
- is a congenital anomaly/birth defect or
- is regarded as medically important without meeting the above-mentioned criteria

14.5. Reporting of Serious Adverse Events

SAEs must be reported by the Investigator within one working day by cell phone and Email to the Clinical Monitor or, if unreachable, other members of the staff at Sponsor or CRO, regardless of the time that may have elapsed from the time the event occurred to when the Investigator first learns of it. The Initial Report should contain at a minimum the following information:

- subject identification
- treatment date

	MGC Pharma Clinical Study Protocol	Protocol No.: MGC-009
		Version 02, 05 Sep 2021
		Page 57 of 76
A Phase IIb, double blind, placebo-controlled clinical study designed to evaluate the effect of CimetrA in patients diagnosed with COVID-19		CONFIDENTIAL

- adverse event symptoms/ diagnosis
- time specification for the medical event
- name of the original reporter

An SAE Report must also be completed, signed and sent to the Clinical Monitor within five working days via fax or regular mail after a direct voice contact. Apart from the information above, the Follow-up Report should also contain the following information based on WHO-UMC system:

- assessment of severity
- assessment of causality

15. MONITORING AND AUDITING PROCEDURES

The study site will be visited by the Clinical Monitor periodically, as agreed upon by the Investigator and MGC-Pharma. It is a function of the Clinical Monitor to ascertain that all aspects of the protocol are complied with and that the conduct of the study conforms to established rules for Good Clinical Practice (GCP).

At the time of each monitoring visit, the Clinical Monitor will review the CRF of the subjects in the study to ascertain that all items have been completed and that the data provided are accurate and obtained in the manner specified in the protocol.

The subject's clinical records will be reviewed to confirm that the protocol has been adhered to with respect to the randomization procedures, subject's information and informed consent, and inclusion/exclusion criteria.

The Clinical Monitor will also check that the data in the CRF are consistent with the clinical records (Source Data Verification) and that study results are recorded completely and correctly. The Monitor will check the reporting of SAEs and the procedures for product accountability and record keeping. For this purpose the

	MGC Pharma Clinical Study Protocol	Protocol No.: MGC-009
		Version 02, 05 Sep 2021
		Page 58 of 76
A Phase IIb, double blind, placebo-controlled clinical study designed to evaluate the effect of CimetrA in patients diagnosed with COVID-19		CONFIDENTIAL

Clinical Monitor must be given direct access to clinical records, original laboratory data, etc., as far as these relate to the study and without jeopardizing subject integrity. CRFs for all included subjects must be made available to the Monitor for review.

The study site may also be subject to Quality Assurance audit by MGC-Pharma. A Regulatory Authority may request to make an inspection of the study site. The procedures of such a visit would be similar to those of a monitoring visit, and data already checked by the Monitor may be checked again. The Investigator is required to inform MGC-Pharma immediately of an inspection requested by a Regulatory Authority.

15.1. **Case Report Forms (CRFs)**

eCRFs of a design mutually agreed upon by the Investigator and MGC-Pharma will be supplied by the contracted CRO. The CRF must be completed and signed for each included subject.

The completed CRFs should be made available for checking of accuracy by the Clinical Monitor as agreed in advance. The original CRFs are the sole property of the MGC-Pharma and should not be copied or made available in any form to a third party, with the exception of authorized representatives of local Regulatory Authorities, without written permission from MGC-Pharma.

15.2. **Source Data**

The printouts from the laboratory analysis will be considered as source and must be labeled with the subject number and measurement period. The printouts must be dated and signed by the Investigator. Results from the blood pressure, heart rate, weight and height measurements are to be recorded directly into the CRF. The subject diary is part of the CRF. Copies of the clinical laboratory and hematology data will be stored in the subject records.

	MGC Pharma Clinical Study Protocol	Protocol No.: MGC-009
		Version 02, 05 Sep 2021
		Page 59 of 76
A Phase IIb, double blind, placebo-controlled clinical study designed to evaluate the effect of CimetrA in patients diagnosed with COVID-19		CONFIDENTIAL

Signed Informed Consent Forms, the existence of medical notes, inclusion/exclusion criteria and AE/SAE will be checked in 100% of the CRFs.

Source data verification

On site subject charts, outside laboratory reports and outside notes, including MD notes, letters and follow-up to subjects/families, are used to verify CRF data. At least 30% of source documents will be verified during the study as follows:

- ☐ 100% of the source documents for the first two visits of the first eight study subjects.
- ☐ 30% source verification for all visits of all subjects.
- ☐ 100% source verification for inclusion/exclusion criteria for all subjects.
- ☐ 100% source verification for adverse event assessment for all subjects.
- ☐ 100% source verification for medication history.

16. STUDY STAFF INFORMATION

It is the responsibility of the Investigator to ensure that all personnel involved in the study are fully informed of all relevant aspects of the study, and have detailed knowledge of and training in the procedures that are to be executed by them. This should be documented in writing stating the time at which training was performed, what was trained, by whom, and who attended.

